Hypothesis: Loteprednol 0.5% gel will perform similarly or better than a regimen of prednisolone acetate 1% and fluorometholone 0.1% in the prevention of visually significant postoperative corneal haze after photorefractive keratectomy (PRK) with a lower incidence of intraocular pressure elevation.

Objectives: We aim to conduct a prospective, randomized trial to compare the incidence of intraocular pressure rise and visually significant postoperative corneal haze after PRK with the use of loteprednol 0.5% gel compared to the use of earlier generation steroids, prednisolone acetate 1% suspension and fluorometholone 0.1% suspension.

Patients undergoing PRK will be assigned to 1 of 2 postoperative steroid regimens. Group 1 will use only loteprednol 0.5% gel, tapered off slowly based on clinical evaluations of the corneal healing response. Group 2 will use prednisolone acetate 1% suspension tapered down to a regimen of fluorometholone 0.1% which will then be tapered off based on clinical evaluations of the corneal healing response. If no difference in efficacy or safety is detected between these two regimens, this study will support the use of either steroid regimen in patients after PRK. If there is a major difference in the efficacy or safety of these two regimens, this could influence post-refractive surgery treatment practices.

7. Is this a multi-site study, where more than one site needs IRB approval?

Yes No

8. Background and Introduction:

In photo-ablation procedures, an excimer laser is used to sculpt corneal tissue to correct refractive error. During PRK, the surface epithelium is removed and the laser energy is applied to reshape the underlying corneal stroma. This procedure is FDA approved and used widely. Corneal haze is a well known and a potentially vision threatening postoperative complication of PRK. Topical ophthalmic corticosteroids are routinely prescribed by most surgeons postoperatively to help prevent this complication.

Desirable characteristics for prophylactic topical steroids to be used after PRK include effective modulation of the healing response to prevent corneal haze while at the same time minimizing side effects, such as intraocular pressure elevation or cataract formation. Loteprednol etabonate is a corticosteroid that exerts its therapeutic effects and is then quickly changed into inactive metabolites by nonspecific esterases found in the cornea [1]. This relatively fast metabolism of loteprednol gives it a lower side effect profile than other steroids, including a smaller effect on intraocular pressure [2, 3]. In the ophthalmic literature, there is currently no consensus on a standard regimen or which type of corticosteroid should be used after PRK.

A retrospective study done at our institution demonstrated a similar incidence of haze and increased intraocular pressure in patients treated with loteprednol 0.5% suspension or fluorometholone 0.1% suspension after both groups received prednisolone acetate 1% suspension for the first 3-4 weeks postoperatively after PRK [4]. This study was limited by its retrospective nature, but was the first study to report the efficacy and noninferiority of loteprednol compared to other steroids for prophylaxis after photorefractive keratectomy. Our current prospective study could help determine whether loteprednol has true advantages over traditional topical steroids after PRK.

References:

4. [name] MD, Leishman LL, Christiansen SM, Sikder S, Hsu M, Moshirfar M. Use of loteprednol for routine prophylaxis after photorefractive keratectomy. Clin Ophthalmol. 2012;6:653-659.

IRB_00075978**Created:** 8/9/2014 9:53 AM**IRB_00075978**

View: 2. Location and Sponsor

PI: [name]

Submitted: 8/20/2014

Title: Efficacy and safety of loteprednol 0.5% gel for routine prophylaxis after photorefractive keratectomy compared to prednisolone acetate 1% suspension and fluorometholone 0.1% suspension

2. Study Location and Sponsors

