Prior to surgery, patients will be randomly assigned to one of two postoperative steroid regimens. Group 1 will use loteprednol 0.5% gel in both eyes, starting at a frequency of four times per day for the first week and then tapered off based on clinical judgement of the corneal healing response. Group 2 will use prednisolone acetate 1% suspension in both eyes, starting at a frequency of four times per day for the first week, then tapered down to a regimen of fluorometholone 0.1% suspension, which will then be tapered off based on clinical judgement of the corneal healing response.

All surgical procedures will be performed according to the standard of care and the surgeons' standard practices. The study outcome measures are standard of care for pre-operative and post-operative evaluation of refractive surgery patients.

The primary outcome measure will be intraocular pressure at each study time point. Secondary outcomes will be grade of corneal haze, manifest refraction, best corrected visual acuity, and uncorrected visual acuity.

Study outcome measures will be evaluated for each treated eye of each subject at each study time point. Routine clinical management may be altered if the intraocular pressure is elevated sufficiently to require medical intervention, if there is significant postoperative corneal haze, or if there are other postoperative complications. In these situations, additional IOP lowering drops may be added or the steroid decreased, changed, or increased, based on the clinical picture and physician judgement. Additional examinations between study time points may be performed as necessary according to the surgeon's usual care, but will not be considered part of the study data. Patients have the right to withdraw at any time and future medical care will not be influenced by their lack of participation.

If enhancement surgery is deemed necessary and performed during the one-year post-operative period, study data collection will end for that eye at the time of the enhancement. All prior data collected will still be included in the statistical analysis and if only one eye requires enhancement, data collection will continue on the fellow eye until the last planned study time point.

Eyes will be evaluated with the following procedures:

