Yes No

If no, list the procedures that are performed for research purposes only (non-standard or non-standard of care procedures):

Only data collection and analysis are for research purposes only. All other procedures are within the standard of care.

8. Is there a safety monitoring plan for this study?

Yes No

9. Provide a summary of the statistical methods, data analysis, or data interpretation planned for this study. Factors for determining the proposed sample size (e.g., power) should be stated.

Standard statistics will be calculated and used to describe the two treatment groups in terms of all study variables: intraocular pressure, grade of corneal haze, manifest refraction, best corrected visual acuity, and uncorrected visual acuity. Statistics will be compiled for each variable at the study time points listed in the data collection protocol. Patients withdrawn from the study prior to surgery will not be included in the data analysis and will be replaced in the enrollment group. For eyes that require enhancement surgery, only data collected prior to the enhancement surgery will be included in the statistical analysis.

Prior studies have considered intraocular pressure elevation of greater than or equal to 10 mm Hg above baseline clinically significant. A prior study of healthy volunteers demonstrated an incidence of IOP elevation > 10 mm Hg of 1.95% in patients using loteprednol eye drops versus 7.48% in patients using dexamethasone eye drops [1]. Using these expected proportions, an alpha of 0.05, and a power of 80%, we would need a sample size of 230 patients (460 eyes). In order to account for about 10% dropout, we intend to enroll 250 patients in the study, 125 in the loteprednol arm and 125 in the prednisolone and fluorometholone arm.

IRB_00075978

Created: 8/9/2014 9:53 AM

IRB_00075978

PI: [name]

Submitted: 8/20/2014

View: 4.2 Consent Process

Title: Efficacy and safety of loteprednol 0.5% gel for routine prophylaxis after photorefractive keratectomy compared to prednisolone acetate 1% suspension and fluorometholone 0.1% suspension

Consent Process

1. The following investigators and internal staff will obtain consent (as indicated on the Study Location and Sponsors Page):

[name] University of Utah

[name]

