IRB_00075978**Created:** 8/9/2014 9:53 AM**IRB_00075978**

View: 6. Risks and Benefits

PI: [name]

Submitted: 8/20/2014

Title: Efficacy and safety of loteprednol 0.5% gel for routine prophylaxis after photorefractive keratectomy compared to prednisolone acetate 1% suspension and fluorometholone 0.1% suspension

6. Risks and Benefits

1. Describe the reasonable foreseeable risks or discomforts to the participants:

This study does not put study participants at any known increased risk beyond that normally assumed by patients undergoing photorefractive keratectomy outside the study, including but not limited to decreased vision, over-correction, under-correction, pain, glare, halos, dry eyes, infection, and corneal haze. The risk of topical steroid-related complications following photorefractive keratectomy, including elevated intraocular pressure, infection, and cataract formation, is assumed by all patients undergoing the procedure at our institution, as it is our routine standard practice to put patients on a tapering regimen of topical steroids post-operatively to decrease the risk of corneal haze.

2. Describe the potential benefits to society AND to participants (do not include compensation):

There may be no direct benefits to participants from their participation in this study. If no difference in efficacy or safety is detected between the two post-operative treatment regimens, this study will support the use of either steroid regimen in patients after PRK. If there is a major difference in the efficacy or safety of these two regimens, this could influence post-refractive surgery treatment practices.

3. Are there any costs to the participants from participation in research?

 Yes No

If yes, specify:

All subjects will be charged the research-discounted price for PRK (\$1200 per eye) and will be responsible for the cost of all necessary medications. Loteprednol is significantly more expensive than prednisolone and fluorometholone. Bausch and Lomb has unconditionally donated loteprednol 0.5% gel for this study, thus patients randomized to the loteprednol arm will be provided this medication without charge. Patients randomized to the prednisolone/fluorometholone arm will be responsible for paying for this medication, just as they would be were they not enrolled in the study.

4. Is there any compensation to the participants?

 Yes No

a. If yes, answer the following:

Specify overall amount:

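### A null result is to count as support for either regimen, but the plan sets no margin or interval criterion, and failing to detect a difference does not show similarity

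*Combined protocol and SAP*

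**What the plan says.** The Hypothesis and Objectives text expects loteprednol to be similar or better on visually significant haze, with less IOP elevation. It then says how a null result will be read: "If no difference in efficacy or safety is detected between these two regimens, this study will support the use of either steroid regimen". Section 6 (Risks and Benefits), item 2, opens the same statement with "If no difference in efficacy or safety is detected between the two post-operative treatment regimens" and reaches the same conclusion. In both places the next sentence says that a major difference could influence practice.

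The statistical text is section 4 (Study Information), item 9. On analysis it says: "Standard statistics will be calculated and used to describe the two treatment groups in terms of all study variables". On sample size it says: "Using these expected proportions, an alpha of 0.05, and a power of 80%, we would need a sample size of 230 patients (460 eyes"), from expected IOP-elevation rates of 1.95% and 7.48%. It names no test and states no margin, confidence-interval criterion or haze rate.

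Two items could be mistaken for a margin. One is the 10 mm Hg threshold: "Prior studies have considered intraocular pressure elevation of greater than or equal to 10 mm Hg above baseline clinically significant". That defines an event in an individual, not a tolerable difference between groups. The other is the word noninferiority in the Background, which describes an earlier retrospective study that "was the first study to report the efficacy and noninferiority of loteprednol compared to other steroids".

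**The concern.** A difference can go undetected because the regimens are alike, or because the trial is too imprecise to separate them. The sentence treats both cases as support for either regimen. Under it, the less precise the trial, the more easily it reaches that conclusion.

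The conclusion would cover IOP elevation, where the plan expects a difference, and haze, which the Background describes as a complication that can threaten vision. For haze, the hypothesis is itself partly one of similarity, so a null haze result is likely to be read through this sentence. Haze is a secondary outcome, and the sample size was not built on it.

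**Working it through.** **Inputs.** Section 4, item 9: rates 1.95% and 7.48%, alpha 0.05, power 80%, 230 patients (460 eyes). The plan does not say whether the test is one- or two-sided; two-sided is assumed because it reproduces the stated size.

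**1. The plan's own figure.** Pooled two-proportion formula:

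n per arm = [1.96·√(2p̄(1−p̄)) + 0.8416·√(p1(1−p1)+p2(1−p2))]² / d²

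- d = 0.0748 − 0.0195 = 0.0553; p̄ = 0.04715.
- √(2p̄(1−p̄)) = 0.2998; √(p1(1−p1)+p2(1−p2)) = 0.2972.
- n = (0.5875 + 0.2501)² / 0.0553² = 229.4, so 230 per arm and 460 in total.

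This matches the stated 460 when the eye is the unit and all eyes are independent. It is a calculation for detecting a difference in IOP elevation.

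**2. Chance of missing the planned difference.** Power = Φ((d − 1.96·√(2p̄(1−p̄)/n)) / √((p1(1−p1)+p2(1−p2))/n)).

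- With n = 230 per arm: (0.0553 − 0.0387)/0.0196 = 0.845 and Φ(0.845) = 0.801, so the miss probability is 0.199, about 20%.

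This is simply the complement of the planned power. It is the most favourable case under this formula, because both eyes of a patient receive the same regimen. At an assumed between-eye correlation of 0.5, the effective n is 230/1.5 = 153.3 and the miss probability is 37%. With 115 patients per arm as the unit it is 49%. The choice between eye and patient is a separate issue, and the present point does not depend on it.

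**3. A null result that does not show similarity.** Take one yes/no outcome per patient, 230/2 = 115 patients per arm, and 2 versus 8 events (loteprednol minus comparator).

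- Rates 1.74% and 6.96%; difference −5.2 points.
- Pooled test: p̄ = 10/230 = 0.0435; standard error √(2 × 0.0435 × 0.9565/115) = 0.0269; z = −1.94; p = 0.052.
- Fisher's exact test: p = 0.10.
- Wilson limits are 0.48% to 6.12% for loteprednol and 3.57% to 13.13% for the comparator. The 95% Newcombe limits are −5.22 − √((1.74−0.48)² + (13.13−6.96)²) = −11.5 points and −5.22 + √((6.12−1.74)² + (6.96−3.57)²) = +0.3 points.

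Neither test is significant at 0.05. The interval contains a 5.53-point difference in loteprednol's favour, which is the difference the trial was sized to find. If no other endpoint differed, the sentence in the objectives would read this result as support for either regimen.

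**4. Haze.** The documents give no expected rate, margin or power, so no document-based figure can be computed.

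**The case against.** The sentence stands in narrative text (objectives and potential benefits), not in the statistical section, and the plan never defines what counts as detecting a difference. The Background says there is no consensus regimen, and section 4 describes all treatments as standard of care. On a softer reading, a null result merely leaves two accepted options in use. That lowers the weight of the point but does not remove it. The sentence says the study will support either regimen, which is more than failing to exclude either. It appears twice, and the statistical section does not qualify it.

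The 20% is not the probability of the stated conclusion. The condition is no difference in efficacy or safety, which spans five outcomes and up to seven postoperative visits; missing all of them is less likely than missing one. The primary outcome in section 4, item 6, is IOP at each time point, and an analysis of IOP as a measurement could have different power. Both limits stand.

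Two stronger readings are tempting. A reader might infer from the 49% that the trial has an even chance of wrongly endorsing both regimens. The documents do not support this: the figure is for one endpoint and rests on the separate question of the unit of analysis. A reader might also infer that a haze non-inferiority test is required. It is not needed to correct the inference, and it may be weak here. With an assumed 5-point margin and 115 patients per arm, its power using Newcombe limits is 56%, 36% and 23% at assumed true haze rates of 2%, 5% and 10%.

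**Conclusion.** The point holds: the plan states a rule for null results that is wrong as written, and nothing in it supplies the margin or interval criterion that a similarity conclusion needs. The logical error rests on no assumed rate.

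Its size can be shown only in part. At the plan's own rates and 80% power, the planned difference in IOP elevation is missed about 20% of the time, and more often if fellow eyes are correlated. This assumes a two-sided pooled test at 0.05 on a single yes/no endpoint. The 2/115 versus 8/115 result is an illustration, not a prediction. The documents do not show that the trial is underpowered for haze, only that they give no basis for judging this. The trial can run as designed. The sentence should be corrected before results are interpreted.

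**What to change.** In the objectives and in section 6, item 2, replace the sentence with: *Failure to detect a difference will not by itself be read as similarity; between-group differences will be reported with 95% confidence intervals.*

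In section 4, item 9, add: *Between-group differences in IOP elevation and visually significant haze will be reported with 95% confidence intervals that allow for paired eyes. A null result whose interval still includes clinically important differences will be reported as inconclusive.*

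Optional: if the investigators want to claim similarity or non-inferiority on haze or IOP, they fix the margin and the event definition before any outcome data by arm are seen, and make the claim only if the interval meets that margin.

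The cost is one sentence replaced in two places and two sentences added. No patients, visits or data are added. The downside is that some results will have to be reported as inconclusive, even where the regimens are in fact equal.

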7. **Select the study procedures that will be conducted at this site:**

There are no items to display

8. **Select the University of Utah department responsible for this research:**

OPHTHALMOLOGY

9. **Add any additional sites that are part of this performance group**

There are no items to display

IRB_00075978**Created:** 8/9/2014 9:53 AM**IRB_00075978**

View: 3. Participants

PI: [name]

Submitted: 8/20/2014

Title: Efficacy and safety of loteprednol 0.5% gel for routine prophylaxis after photorefractive keratectomy compared to prednisolone acetate 1% suspension and fluorometholone 0.1% suspension

3. Participants

1. Ages of Participants:

18 and older (Consent form needed)

2. Specific age range of participants (e.g., 7-12 years old, 60+, etc.):

21+

3. Indicate any vulnerable participant groups (other than children) included:

None

If 'Other', please specify:**If 'None' and no children are involved, answer the following question.****Has the participant selection process overprotected potential subjects who are considered vulnerable so that they are denied opportunities to participate in research?** Yes No**4. Number of participants to be included and/or enrolled in this entire study, across all study locations:** 250**At Utah prior to October 2019:** 250**5. Characteristics of Participants/Inclusion Criteria:**

All subjects who are deemed suitable candidates for PRK after routine refractive surgery screening will be considered eligible for participation in this study. Subjects must be at least 21 years of age and not pregnant or nursing (due to fluctuations in visual parameters during pregnancy).

6. Participant Exclusion Criteria:

Selection will be consistent with the current standard of care for PRK. Any patient that is not a suitable candidate for PRK will not be included.

7. Is a substantial percentage of the participant population anticipated to be non-English speaking? Yes No

IRB_00075978**Created:** 8/9/2014 9:53 AM**IRB_00075978**

View: 4. Study Information

PI: [name]

Submitted: 8/20/2014

Title: Efficacy and safety of loteprednol 0.5% gel for routine prophylaxis after photorefractive keratectomy compared to prednisolone acetate 1% suspension and fluorometholone 0.1% suspension

4. Study Information

1. Design of Study (select all that apply):

Non-Experimental and/or Descriptive Research Design:

There are no items to display

Experimental and/or Interventional Research Design:

Prospective Biomedical Intervention or Experiment
Randomized Trial

Development of a research resource (repositories, databases, etc.)

Other

2. Does your study involve the use of any placebo?

Yes No

3. Length of entire study, from initiation through closeout:

2 years

4. How will participants be recruited or identified for inclusion in the study?

a. **Select all methods that will be used:**

In-person contact (e.g., patients, students, etc.)

Written advertising (flyers, brochures, website postings, newspaper ads, etc.)

Other

Information will be included on the Moran Eye Center website, Moran Eye Center Facebook, and Moran Eye Center Twitter account.

Http://healthcare.utah.edu/moran/patient_care/refractive_surgery_lasik

<Https://www.facebook.com/moraneyecenter>

<Https://twitter.com/moraneyecenter>

b. **Describe the recruitment/participant identification process in detail (e.g. who will review charts or records, who can refer participants to the study, where will flyers be posted, how often will recruitment letters be sent, when will follow-up phone calls be made, etc.):**

Patients requesting refractive surgery will be informed about the study and asked if they would like to participate. Advertisements will also be included on the Moran Eye Center website, Facebook page, and Twitter account, as well as in newsprint.

5. How will consent be obtained?

Informed Consent Process (with or without a document)

6. Describe all the procedures chronologically, from screening/enrollment through study closeout, which will be completed in the research project.

Patients who are interested and eligible to participate in this study will be enrolled and will read and sign the study informed consent prior to surgery. As is standard for our PRK cases, they will also be required to watch an informational video, read and sign the "Consent to Have Refractive Surgery" and respond to a brief test concerning its content.

Prior to surgery, patients will be randomly assigned to one of two postoperative steroid regimens. Group 1 will use loteprednol 0.5% gel in both eyes, starting at a frequency of four times per day for the first week and then tapered off based on clinical judgement of the corneal healing response. Group 2 will use prednisolone acetate 1% suspension in both eyes, starting at a frequency of four times per day for the first week, then tapered down to a regimen of fluorometholone 0.1% suspension, which will then be tapered off based on clinical judgement of the corneal healing response.

All surgical procedures will be performed according to the standard of care and the surgeons' standard practices. The study outcome measures are standard of care for pre-operative and post-operative evaluation of refractive surgery patients.

The primary outcome measure will be intraocular pressure at each study time point. Secondary outcomes will be grade of corneal haze, manifest refraction, best corrected visual acuity, and uncorrected visual acuity.

Study outcome measures will be evaluated for each treated eye of each subject at each study time point. Routine clinical management may be altered if the intraocular pressure is elevated sufficiently to require medical intervention, if there is significant postoperative corneal haze, or if there are other postoperative complications. In these situations, additional IOP lowering drops may be added or the steroid decreased, changed, or increased, based on the clinical picture and physician judgement. Additional examinations between study time points may be performed as necessary according to the surgeon's usual care, but will not be considered part of the study data. Patients have the right to withdraw at any time and future medical care will not be influenced by their lack of participation.

If enhancement surgery is deemed necessary and performed during the one-year post-operative period, study data collection will end for that eye at the time of the enhancement. All prior data collected will still be included in the statistical analysis and if only one eye requires enhancement, data collection will continue on the fellow eye until the last planned study time point.

Eyes will be evaluated with the following procedures:

- Intraocular pressure (by applanation tonometry): Pre-operatively and post-operative week 1 (\pm 3 days), month 1 (\pm 10 days), month 2 (\pm 10 days), month 3 (\pm 14 days), month 6 (\pm 1 month), and month 12 (\pm 1 month)

Note: Intraocular pressure will be measured by a technician or physician who is masked to the treatment regimen of the patient at each visit.

- Grade of corneal haze (Fantes scale): Post-operative Month 1 (\pm 10 days), month 2 (\pm 10 days), month 3 (\pm 14 days), month 6 (\pm 1 month), and month 12 (\pm 1 month)

Note: Corneal haze will be graded by a study physician who did not perform the original surgery and is masked to the treatment regimen of the patient at each visit.

- Manifest refraction (sphere, cylinder, and axis): Pre-operatively and post-operatively month 1 (\pm 10 days), month 2 (\pm 10 days), month 3 (\pm 14 days), month 6 (\pm 1 month), and month 12 (\pm 1 month)

- Best corrected visual acuity: Pre-operatively and post-operatively month 1 (\pm 10 days), month 2 (\pm 10 days), month 3 (\pm 14 days), month 6 (\pm 1 month), and month 12 (\pm 1 month)

- Uncorrected visual acuity: Pre-operatively and post-operative day 1 (\pm 1 day), week 1 (\pm 3 days), month 1 (\pm 10 days), month 2 (\pm 10 days), month 3 (\pm 14 days), month 6 (\pm 1 month), and month 12 (\pm 1 month)

- Pupil size measured in the dark: Pre-operatively only

- Corneal pachymetry: Pre-operatively only

Data and Safety Monitoring:

There is no formal data and safety monitoring board for this study. All treatments, procedures, and testing being performed in the study are within the standard of care and treatment for PRK patients. This study does not put study participants at any known increased risk beyond that normally assumed by patients undergoing PRK outside the study. The investigators feel that the standard processes for identifying and reporting adverse events (AE) are sufficient to safeguard the well-being of study participants.

The investigators have a nomogram from which they work and therefore have expected vision outcomes for patients on an individual basis. It is routine practice to compare actual with expected outcomes as a quality assurance measure. Should any concerns arise prior to completion of the study, a safety analysis will be conducted immediately.

For this protocol, an AE is any "on study" untoward medical occurrence (e.g., sign, symptom, disease, syndrome, intercurrent illness) that is experienced by a study subject, regardless of the suspected cause. Both serious and non-serious AEs will be graded on a three-point scale (mild, moderate, severe), and the investigators will assess whether there is a reasonable possibility that study procedure caused or contributed to the AE.

Adverse events that start on Day 0 (Surgery) through the last study visit will be recorded on the study AE log and described in detail in the patient chart. Subjects discontinued early from the study due to an adverse event will be asked to return for a final evaluation. All study-related adverse events will be followed until resolution (or determined to be irreversible, chronic, or stable).

Adverse events that are determined to be unexpected, possibly related to the study procedure, and place subjects at increased risk, will be reported to the Institutional Review Board (IRB) according to their guidelines.

Standard of Care / Research Costs:

All procedures are considered within the standard of care for PRK surgery and will be billed to patients in the usual manner; however, participants will be eligible for a reduced study fee for their surgery and post-operative care. PRK surgery is considered cosmetic surgery and is never billed to insurance. The refractive surgery charge includes standard post-operative examinations up to one year.

Loteprednol 0.5% gel is not available in a generic formulation and is therefore significantly more expensive than generic prednisolone acetate 1% suspension and fluorometholone 0.1% suspension. A request for a donation of loteprednol 0.5% gel for this study has been submitted to Bausch and Lomb and is currently under review. If approved, this drug donation will allow us to eliminate the additional expense of a branded drug for patients that are randomized to the loteprednol group.

If enhancement surgery is deemed necessary during the one-year post-operative period, this will be included based on the patient's initial fee, as is standard of care. Any other costs related to management of adverse events, or if additional refractive correction is necessary at some time after the one-year postoperative period, will remain the patient's responsibility and are not included in the study surgery fee.

7. Are all procedures for research purposes only (non-standard or non-standard of care procedures)?

Yes No

If no, list the procedures that are performed for research purposes only (non-standard or non-standard of care procedures):

Only data collection and analysis are for research purposes only. All other procedures are within the standard of care.

8. Is there a safety monitoring plan for this study?

Yes No

9. Provide a summary of the statistical methods, data analysis, or data interpretation planned for this study. Factors for determining the proposed sample size (e.g., power) should be stated.

Standard statistics will be calculated and used to describe the two treatment groups in terms of all study variables: intraocular pressure, grade of corneal haze, manifest refraction, best corrected visual acuity, and uncorrected visual acuity. Statistics will be compiled for each variable at the study time points listed in the data collection protocol. Patients withdrawn from the study prior to surgery will not be included in the data analysis and will be replaced in the enrollment group. For eyes that require enhancement surgery, only data collected prior to the enhancement surgery will be included in the statistical analysis.

Prior studies have considered intraocular pressure elevation of greater than or equal to 10 mm Hg above baseline clinically significant. A prior study of healthy volunteers demonstrated an incidence of IOP elevation > 10 mm Hg of 1.95% in patients using loteprednol eye drops versus 7.48% in patients using dexamethasone eye drops [1]. Using these expected proportions, an alpha of 0.05, and a power of 80%, we would need a sample size of 230 patients (460 eyes). In order to account for about 10% dropout, we intend to enroll 250 patients in the study, 125 in the loteprednol arm and 125 in the prednisolone and fluorometholone arm.

IRB_00075978

Created: 8/9/2014 9:53 AM

IRB_00075978

PI: [name]

Submitted: 8/20/2014

View: 4.2 Consent Process

Title: Efficacy and safety of loteprednol 0.5% gel for routine prophylaxis after photorefractive keratectomy compared to prednisolone acetate 1% suspension and fluorometholone 0.1% suspension

Consent Process

1. The following investigators and internal staff will obtain consent (as indicated on the Study Location and Sponsors Page):

[name] University of Utah

[name]

[name] University of Utah

[name] University of Utah

List by name, role, and affiliation any others who will obtain consent (e.g. [name], Co-Investigator, etc.).

2. Describe the location(s) where consent will be obtained.

Moran Eye Center Clinics

3. Describe the consent process(es), including the timing of consent. Describe whether there is a waiting period between the consent process and obtaining consent from the participant (i.e., any time between informing participants and actually obtaining consent).

All of our standard evaluation and consent processes for refractive surgery will be followed. Patients who are interested in refractive surgery undergo a standard refractive surgery screening examination with the surgeon, during which their candidacy for refractive surgery is determined and the risks and benefits of all potential refractive procedures for which they medically qualify, which may or may not include PRK, are discussed. Patients who are not already aware of the study are also informed about the possibility of participating in the study during or prior to this first clinic visit. Patients who are good candidates medically and motivated to undergo surgery are then scheduled for a repeat examination to ensure refractive and keratometric stability, as well as to further discuss and finalize the surgical plan based on the patient's goals and clinical findings, as is our usual standard. If a patient is deemed medically eligible for and chooses to undergo PRK, they may choose to be included in the study. The study risks and benefits will be discussed and patients will be given opportunities to ask questions regarding the study at any of the clinic visits described above. Consent will be signed by the patient prior to undergoing surgery.

4. Describe what measures will be taken to minimize the possibility of coercion or undue influence.

Patients interested in refractive surgery are screened and, based on clinical findings, the screening surgeon presents them with the risks and benefits of all procedures for which there are good candidates, which may or may not include PRK. All patients are free to undergo the refractive procedure that is best suited to them, including PRK, without participating in the study.

5. Describe the provisions that are made to allow adequate time to exchange information and questions between the investigator and participant.

All study participants will meet with their surgeon on at least 3 occasions prior to undergoing surgery. This includes the initial refractive surgery screening, repeat exam, and on the day of surgery prior to the procedure. Patients will have the opportunity to discuss the study and surgical plan at any of these visits.

6. Will a legally authorized representative (LAR) be used?

Yes No

7. Will a language other than English be used to obtain consent?

Yes No

8. **Are you requesting that documentation of informed consent be waived by the IRB (a consent process in place, but no documentation of consent, e.g. questionnaire cover letter, web-based consent, consent without signature, etc.)?**

Yes No

If yes, complete the following:

a. **Explain why the waiver of consent documentation is being requested.**

b. **Justification for the waiver is one of the following:**

There are no items to display

IRB_00075978**Created:** 8/9/2014 9:53 AM**IRB_00075978**

View: 5. Data Monitoring Plan

PI: [name]

Submitted: 8/20/2014

Title: Efficacy and safety of loteprednol 0.5% gel for routine prophylaxis after photorefractive keratectomy compared to prednisolone acetate 1% suspension and fluorometholone 0.1% suspension

5. Data Monitoring Plan

1. Privacy Protections: Privacy refers to persons and to their interest in controlling access of others to themselves. Privacy can be defined in terms of having control over the extent, timing and circumstances of sharing oneself (physically, behaviorally, or intellectually) with others. **What precautions will be used to ensure subject privacy is protected?**

Select all that apply:

The research intervention is conducted in a private place

Discussing the study with participants individually instead of in front of a group

The collection of information about participants is limited to the amount necessary to achieve the aims of the research, so that no unneeded information is being collected

Other or additional details (specify):

Other or additional details (specify):

